5.7 Withdrawal of Subjects

Subjects will be told that they may withdraw from the study at any time. As soon as the subject notifies the PI or researcher that they wish to cease their participation in the study, any appointments will be canceled and the participant will be paid for any sessions partially or fully completed.

Participants may be withdrawn without their consent if the study is suspended during their participation or they suffer a health-related event within the time frame of their participation that precludes them from participating further, including complications from surgery.

6.0 Reporting

Adverse Event (AE): If a research participant exhibits acute discomfort as noted by the researcher during a testing session (e.g., expressing discomfort or overwhelming disorientation while standing on the VETS apparatus), they will be asked if they feel they are able to carry on with the session and offered a break. If they are unable to carry on, the PI will be informed immediately and the testing session will be terminated for the day.

Serious Adverse Event (SAE): An example of a SAE would be a participant suffering severe complications associated with the CSM surgical treatment. It is likely that such complications will occur only unrelatedly to any study activities—especially if a participant is prohibited from active participation while experiencing such complications. In the event that a participant has a strongly negative response to the surgery, the participant will not be scheduled for any post-surgical appointments.

An AE temporally related to participation in the study will be documented whether or not considered related to the test article or procedure. This definition includes current illnesses and injuries and exacerbations of preexisting conditions including changes to psychological state. AE will be kept in the subject tracking log and reported as a summary at continuing review. Expected adverse events which are not serious are reported on the Continuing Review Progress Report (CR). Any unanticipated adverse event related to application of tDCS will be reported to the IRB within 10 days, as per Federal Regulations Title 21 812.150 (1).

SAE, such as hospitalization for more than 24 hours, will be reported to the IRB within 5 days per SOP 151-17. This will be accomplished by submitting an adverse event report to the IRB.

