5.0 Study Procedures

5.1 Study Design

For AIM 1, a cross-sectional design that includes within-subjects (VETS conditions) and between-subjects (veteran groups) factors will be used to compare balance and posture in patients awaiting surgery for CSM ($n = 20$) to a cohort of age and gender-matched non-CSM controls ($n = 20$). The 20 veterans with CSM recruited for AIM 1 will also serve as the sample for AIM 2, which is a longitudinal assessment of balance following surgical intervention for CSM. The data generated from the proposed study will provide a base estimate of the variance in our veteran groups for use in the power calculation for a larger follow up study

Veteran volunteers (CSM and control) meeting eligibility criteria will complete one session of VETS balance testing. Those veterans awaiting surgery for CSM will be asked to return for three additional sessions of VETS at designated time points scheduled 2 weeks, 6 weeks, and 6 months post-surgery. For returning CSM veterans, self-report measures will be collected at each additional time point to compare objective (VETS) and subjective (scale measures) assessments of functional impairment related to CSM following surgery. None of the procedures involved in this research project will alter standard of care associated with CSM or the surgical treatment. “Each patient will be cleared by one of the study doctors ([name], [name], or [name]) before participating in the post-surgery sessions. In the event that a patient is found to be physically incapable of safely participating in the first post-surgery session, they will not continue participation in the study until they are cleared by the study doctors. Thus, even if a patient is not cleared to participate in the two week post-surgery time point, they may be cleared to participate in the remaining two sessions (six weeks and six months post-surgery).”

Risks/Benefits of Participation

There are no risks associated with the questionnaires included in this study, as they ask only about physical symptoms and functioning associated with CSM. Although some emotional health questions will be included, they are not expected to be upsetting in any capacity.

The risks associated with VETS testing are minimal and are as follows:

- Discomfort from standing on the WBB or foam for a prolonged period of time
- Dizziness or disorientation when viewing the dynamic condition

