Initial Testing Session: For all participants, the first session will involve obtaining informed consent and HIPAA authorization, completing self-report questionnaires, and a session of VETS testing. This initial session will last approximately 60 minutes. The informed consent procedure will follow the description outlined in section 5.3 and is expected to take around 15 minutes. Subsequently, the participant will fill out all listed self-report questionnaires, which will take about 15 minutes. Lastly, the participant will undergo one session of VETS testing, which will take about 20 minutes. VETS testing will follow the protocol outlined above in the “Materials” section. For CSM patients, one of the study doctors will fill out the clinical assessments during standard of care appointments throughout the study that correspond in time with the participant’s research appointments.

All subsequent sessions (2, 3, & 4) will include CSM participants only, and will be conducted after surgical treatment.

Testing Session 2: Participants will be scheduled for the second testing session 2 weeks post-surgery. This session will include all self-report questionnaires except demographics and a session of VETS testing. It will last approximately 30-45 minutes.

Testing Session 3: Participants will be scheduled for the second testing session 6 weeks post-surgery. This session will include all self-report questionnaires except demographics and a session of VETS testing.

Testing Session 4: Participants will be scheduled for the second testing session 6 months post-surgery. This session will include all self-report questionnaires except demographics and a session of VETS testing.

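### Sections 5.1 and 6.0 can send the same patient with a surgical complication to opposite outcomes, and the Section 6.0 rule removes patients from AIM 2 and the questionnaires according to their response to surgery

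*Combined protocol and SAP*

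**What the plan says.** Three places in the protocol govern what happens when a CSM patient does badly after surgery.

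Section 5.1 (Study Design) requires clearance by a study doctor before the post-operative sessions. Of patients who cannot safely do the first one it says "they will not continue participation in the study until they are cleared by the study doctors". It then says that, even so, "they may be cleared to participate in the remaining two sessions (six weeks and six months post-surgery").

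Section 5.7 (Withdrawal of Subjects) allows removal without consent if the study is suspended or if the patient has a "health-related event within the time frame of their participation that precludes them from participating further, including complications from surgery". The wording is permissive.

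Section 6.0 (Reporting), in the paragraph on serious adverse events, reads: "In the event that a participant has a strongly negative response to the surgery", "the participant will not be scheduled for any post-surgical appointments". The sentence just before it refers to a bar on active participation only for as long as the complications last.

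Under Section 5.5, each post-operative session combines the self-report questionnaires (NDI, SF-36) with VETS testing. No questionnaire-only visit, telephone or mail route is described. The mJOA and Nurick scales are handled separately: a study doctor is to "fill out the clinical assessments during standard of care appointments throughout the study that correspond in time with the participant’s research appointments".

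**The concern.** The hold in Section 5.1 is reversible and the bar in Section 6.0 is not. No text says where a patient not yet cleared ends and a patient with a strongly adverse response begins, or which section prevails. Two staff members could treat the same event differently and both be following the protocol.

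The Section 6.0 trigger is the response to surgery, and AIM 2 exists to measure the response to surgery: Hypothesis 4 expects sway to fall. A rule that stops follow-up because surgery went badly selects the AIM 2 sample on something close to its outcome. It also closes the appointment at which NDI and SF-36 would be collected, although those forms need no standing and the physical risks listed in Section 5.1 come from standing on the board or foam and viewing the moving scene. Post-operative time points that are not observed cannot be recovered later.

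**Working it through.** The documents give no complication rate, dropout rate or effect size, so there is no figure of the plan's own to reproduce. The check is a comparison of texts followed by a count.

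**1. The rules side by side.**

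| | Section 5.1 | Section 5.7 | Section 6.0 |
|---|---|---|---|
| Trigger | Physically unable to do the first post-operative session safely | Health event that rules out further participation, surgical complications included | Strongly adverse response to surgery, undefined |
| Force | Mandatory hold | Discretionary | Mandatory |
| Duration | Until cleared | Permanent once applied | All post-operative appointments |
| Decider | Study doctors | Not stated | Not stated |

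**2. One patient through the rules.** Suppose a complication ten days after surgery that has resolved by week 6.
- Section 5.1: the 2-week session is missed; the 6-week and 6-month sessions can go ahead once the patient is cleared.
- Section 6.0, if the event is judged a strongly adverse response: none of the three sessions is scheduled.
- Section 6.0, preceding sentence: the bar would end when the complication ends, which agrees with Section 5.1 and not with the sentence that follows it.
- Section 5.7: either result, because withdrawal is optional.

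**3. Sessions at stake.** Inputs: 20 CSM patients and 3 post-operative sessions each (Section 5.1), so 20 × 3 = 60 sessions. The complication rate is an assumption, 5% to 20%.
- Patients affected: 0.05 × 20 = 1 to 0.20 × 20 = 4.
- Lost under Section 6.0: 1 × 3 = 3 to 4 × 3 = 12 of 60.
- Lost under Section 5.1 if only the first session is missed: 1 × 1 = 1 to 4 × 1 = 4 of 60.
- Depending only on which section is applied: 3 − 1 = 2 to 12 − 4 = 8 of 60.

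A patient who is never cleared loses all three sessions under Section 5.1 as well, so the gap between the rules concerns patients who recover in time for a later visit.

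**4. Direction of the selection (illustration only).** Take 20 standard-normal changes and drop the k worst. The mean of those kept shifts by the sum of the k largest expected values divided by (20 − k). By simulation (200,000 samples of 20), the kept patients look better by about 0.10 SD for k = 1, 0.18 SD for k = 2 and 0.33 SD for k = 4. If the tendency to be dropped correlates only 0.5 with the change, the shifts halve to about 0.05, 0.09 and 0.17 SD. The documents do not say how closely a bad surgical response tracks the change in sway, so this shows direction and a plausible scale, not an estimate.

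**The case against.** The strongest reply is that the triggers differ and the rules form graded steps: a pause for a patient who cannot yet stand safely, optional withdrawal for an event that rules out continuing, and no scheduling after a severe one. This stands in part. Section 5.7 is permissive and contradicts neither of the other two, so a reader who infers three mutually contradictory rules goes further than the text. But no threshold or ranking supports the graded reading, and it does not explain the change of duration within Section 6.0.

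Other inferences are tempting and are not supported:

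- That every rule ends all data collection. The Section 5.1 hold is temporary and costs only the visits before clearance. Only Section 6.0, or Section 5.7 when it is used, removes everything that remains.
- That no one decides. Section 5.1 gives the study doctors the clearance decision for the post-operative sessions. Only the removal decisions in Sections 5.7 and 6.0 lack a named role.
- That safety follow-up is lost. Sessions 2 to 4 contain questionnaires and VETS and no described safety assessment. Section 5.1 leaves standard of care unaltered, and Section 6.0 keeps its tracking log and its 5-day IRB report for serious events.
- That mJOA and Nurick are lost. They are completed at routine visits and nothing stops that. What is missing is a statement that they remain study data after a hold.
- That keeping the questionnaires rescues the comparison of VETS with the scales. Without a VETS value at that visit there is nothing to compare. Section 5.6 specifies no post-operative analysis of NDI or SF-36; AIM 2 enters VETS measures only.

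One further limit: AIM 2 is a repeated-measures ANOVA without imputation. Run conventionally on complete cases, it would drop a patient who missed even one session under either rule. The later sessions preserved by Section 5.1 then help only in summaries or analyses that can use incomplete patients. That modelling question is separate from this point.

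**Conclusion.** The concern holds as a conflict between Sections 5.1 and 6.0 and within Section 6.0, with Section 5.7 adding an unassigned discretionary removal. Followed as written, Section 6.0 removes patients according to their response to surgery, including some who could later be cleared under Section 5.1.

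The size cannot be derived from the documents. The 3 to 12 of 60 sessions under Section 6.0 rest on the assumed 5% to 20% rate and on every such event being classed as a strongly adverse response. The 1 to 4 of 60 under Section 5.1 rest on the same rate and on return at the 6-week session. Each patient affected is 1/20 = 5% of the AIM 2 sample.

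This does not invalidate a 40-person pilot. It is worth correcting before patients reach surgery, because the study is meant to supply variance estimates for a larger one. Which clinical rule should apply is not judged here.

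**What to change.** Reconcile Sections 5.1, 5.7 and 6.0 into one rule that defines its triggers, says whether and how a patient can return, and names one deciding role. The clinical content of the rule is for the sponsor to set.

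Separately, state in Section 5.5:

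- A patient who is not cleared for VETS, has not withdrawn consent, and is able and willing still completes NDI and SF-36 at 2 weeks, 6 weeks and 6 months, by telephone or mail if needed.
- mJOA and Nurick scores recorded at standard-of-care visits remain study data for that patient.
- The reason VETS was not done is logged at each missed session.

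These data describe the patients absent from the AIM 2 analysis and let a reader judge how selected the remainder is. They do not stand in for the missing VETS values.

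The cost is a protocol amendment, consent wording for remote questionnaires, and some coordinator time. No new instruments or staff are needed. The burden on an unwell patient is the reason for making completion depend on being able and willing.

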4.0 Resources and Personnel

All research activities will be conducted at the Syracuse VA Medical Center, using equipment already owned by the PI. All research activities and data storage will take place in the D-wing of the SVAMC. Potentially eligible CSM patients will be identified by Drs. [name], [name], and [name] during CSM surgery scheduling and referred to the study coordinator. Interested patients will be screened additionally and scheduled for an appointment if they are eligible. The study coordinator will consent the participants and obtain HIPAA authorization before collecting study data. Collecting study data will involve administering questionnaires and VETS testing. Drs. [name] and [name] will complete the clinical scales being used in the study. [name] will process VETS data and [name] will run all statistical analyses.

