Demographics: The demographics form will ask about basic information, including: age, sex, history of head injury, and current medications.

VETS. Postural stability will be assessed with the VETS system devised by [name] ^{31, 38-40}. All postural conditions are performed in a darkened room. The physical set-up has the front edge of the Wii balance board (WBB) placed at a distance of 40 cm from a 60" commercially-available flat screen television. This device employs a custom-designed software user interface that allows wireless Bluetooth collection of

center-of-pressure data at 100 Hz with high test-retest reliability and immediate display of results. Excellent concurrent validity was determined by comparing VETS with a research grade gold-standard NeuroCom, which revealed $ICC > 0.90$ (min: 0.901, max: 0.995, $p < 0.01$).

The postural stability task will involve six conditions during which veterans are instructed to look straight ahead and maintain an upright stance as stably as possible (see Figure 2). Veterans are barefooted with feet comfortably placed ~25 cm apart. The six conditions are (1) Eyes Open (EO) Firm – eyes open with stable support surface (i.e. WBB) and static visual scene, (2) Eyes Closed (EC) Firm – eyes closed with stable support surface and dark screen, (3) Dynamic Scene (DYN) Firm – eyes open with a stable support surface while viewing a scene dynamically rotating in the roll (fronto-parallel) plane at 60 deg/s, (4) EO Foam - eyes open with unstable support (Airex foam pad placed on top of the WBB) and stable visual scene, (5) EC Foam – eyes closed with unstable support and dark screen, and (6) DYN Foam – eyes open with unstable support and rotating scene. Each condition lasts 30 secs and is repeated 3 times before progressing to the next condition. The conditions are tested in order 1-6, in a manner that emulates the validated Sensory Organization Test (SOT) protocol (Natus/Neurocom). For safety, an experimenter guards the veteran to protect against falls.

B. Procedure

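### The 10-day IRB reporting rule for unanticipated adverse events is tied to tDCS, which the protocol mentions nowhere else, so as written it covers no event in this study

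*Combined protocol and SAP*

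**What the plan says.** Section 6.0 of the combined protocol and SAP describes how adverse events reach the IRB. There are four routes.

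- All adverse events: "AE will be kept in the subject tracking log and reported as a summary at continuing review".
- Expected events that are not serious: the Continuing Review Progress Report.
- Unanticipated events: "Any unanticipated adverse event related to application of tDCS will be reported to the IRB within 10 days". A federal regulation is cited for this deadline.
- Serious events: "SAE, such as hospitalization for more than 24 hours, will be reported to the IRB within 5 days per SOP 151-17".

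The section also has an internal step for a participant in acute discomfort during testing: "If they are unable to carry on, the PI will be informed immediately and the testing session will be terminated for the day".

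On what is done to participants, Section 4.0 states: "Collecting study data will involve administering questionnaires and VETS testing". Sections 4.0 and 5.5 add clinical scales completed by study doctors.

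On risk, Section 5.1 introduces its list with "The risks associated with VETS testing are minimal and are as follows". Two items follow: discomfort from prolonged standing, and dizziness or disorientation with the dynamic scene. Falls are not an item. The text directly after the list nevertheless speaks of reducing the chance of a fall and of spotting by a trained experimenter. Section 5.5 repeats the precaution: "For safety, an experimenter guards the veteran to protect against falls".

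**The concern.** The 10-day sentence is an operative safety rule, with a trigger, a deadline and a legal citation. Its trigger is a procedure that does not belong to this study. Staff who followed it literally would have no duty under it for anything that happens during VETS testing.

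What is at stake is how soon the IRB learns of something unforeseen. The population has impaired balance by hypothesis, is tested with eyes closed and on foam, and returns for testing after surgery. An unforeseen reaction to testing that falls short of serious is what a prompt-report rule for unanticipated events is there to catch.

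**Working it through.** No calculation applies. The only figures are two deadlines, 10 days and 5 days, which are rules and not derived quantities. The check sets the sections side by side.

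**Step 1. Is tDCS part of the study?** It is absent from the abstract, the introduction, the objectives (3.0), the design and risk text (5.1), the materials and session descriptions (5.5) and the analysis (5.6). The abbreviation list goes from TBI straight to VETS, with no entry for tDCS. The four testing sessions in 5.5 contain questionnaires and VETS, with consent and demographics at the first. Section 6.0 is the only place where the term occurs.

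**Step 2. Where does each class of event go?**

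| Class of event | Route in 6.0 | IRB deadline | Possible in this study? |
|---|---|---|---|
| Serious | Adverse event report to the IRB | 5 days | Yes |
| Expected, not serious | Continuing Review Progress Report | None in days | Yes |
| Unanticipated, tDCS-related | Report to the IRB | 10 days | No |
| Unanticipated, not serious, VETS-related | Tracking log and continuing-review summary only | None in days | Yes |

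The third row is empty. The fourth row is the class that the 10-day rule would cover if it named the study's own procedure. Notice to the PI does not fill the gap, because it is internal and carries no IRB deadline.

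**Step 3. How would a non-serious fall be classed?** Two readings are open.

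- Going by the two-item list in 5.1, a fall is not a listed risk and might be called unanticipated.
- Going by the text after that list and by 5.5, falls are foreseen and guarded against, so a fall might be called expected.

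As 6.0 now stands, the choice makes no difference to timing: both readings end at continuing review. Once the 10-day sentence names VETS testing, they part. The first leads to a 10-day report and the second to continuing review. Correcting the sentence therefore makes it necessary to settle the classification.

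**The case against.** **Falls are foreseen.** A reader might infer that the protocol leaves falls, as unanticipated events, with no prompt route. The documents do not support that. Sections 5.1 and 5.5 both provide against falls, so a non-serious fall can fairly be read as expected and would go to continuing review even if the tDCS wording were corrected. Adding falls to the risk list would confirm that routing. This objection stands, and the point does not rest on falls. What remains is that the list and the precautions do not agree, so the class is unclear.

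**Events are not lost.** A reader might also infer that VETS events go unreported. They do not. Section 6.0 requires documentation of any event temporally related to participation, whether or not it is judged related to the procedure. Serious events have the 5-day route. A study doctor clears each patient before post-surgery sessions, and entry to the CSM group requires unsupported standing with eyes closed for 30 seconds. All of this stands and limits the consequence. None of it supplies an IRB deadline for an unanticipated, non-serious event.

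**Other rules may apply.** Section 6.0 relies on SOP 151-17 and cites a federal regulation, and neither is reproduced. The part of the document between the title and Section 2.0 was not available to this review. A duty may exist elsewhere, so the supportable statement is that this protocol states no expedited route, and not that none exists.

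**It is only a slip.** The sentence may have been carried over from another protocol; that is an inference. Even so, it is the only 10-day rule in the document, and it is the text that study staff would work from.

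**Conclusion.** The sentence is wrong as written. One of the four reporting routes in Section 6.0 applies to no event in this study. As a result, one class of event that can occur (unanticipated, non-serious, VETS-related) has no stated expedited IRB route.

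The practical size cannot be given as a number. The documents contain no rate of falls or of other adverse events, so counts of sessions or trials would show exposure and not the number of reports affected. They also give no interval for continuing review, so the length of the delay is unknown. No aim, endpoint, sample size or analysis is affected.

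The conclusion rests on two assumptions: that tDCS is also absent from the part of the document not available here, and that 6.0 is applied as worded.

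**What to change.** Amend the 10-day sentence in Section 6.0 so that it refers to the procedure this study uses, either VETS testing or the study procedures generally.

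In the same amendment, reconcile the two-item risk list in Section 5.1 with the fall precautions in 5.1 and 5.5. State whether a non-serious fall during testing counts as expected, and name the reporting route that follows. Adding falls to the list without naming the route would send them to continuing review by default; the sponsor should make that choice openly.

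The cost is a wording amendment. No procedure, visit or analysis changes.
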